11 STUDY PARTICIPANTS SELECTION

11.1 Inclusion Criteria

To be included in the study, the patient must meet all the following criteria:

- Signed informed consent form
- Female aged 18 years old or above
- Bilateral breast cancer
- Needing bilateral mastectomy for breast cancer or for risk reduction (due to pathological

gene mutation or high-risk family history or previous mantle radiotherapy for lymphoma)

- Undergoing bilateral mastectomy concurrently with immediate breast reconstruction
- Undergoing the same type of breast reconstruction on both sides
- Adequate liver function where bilirubin is ≤1.5 x ULN
- Adequate renal function with a serum creatinine \leq 1.5 x ULN
- Willing and able to comply with scheduled visits and study procedures for the duration of the study.

11.2 Exclusion Criteria

The presence of any of the following will exclude patients:

- Unilateral breast cancer
- Undergoing unilateral mastectomy
- Not undergoing immediate breast reconstruction
- Locally advanced breast cancer with skin involvement
- Previous unilateral breast radiotherapy (if mastectomy is for local recurrence)
- Previous significant unilateral breast surgery (such as reduction) judged by the recruiting/operating surgeon to have adversely affected breast supply on that side
- Known allergies or hypersensitivity to indocyanine green (ICG) dye, sodium iodide or iodine or having experienced previous side-effects of ICG dye or its components
- Patients with an overactive thyroid or benign tumours of the thyroid gland
- Patients with severe renal insufficiency
- Women who are pregnant, plan to become pregnant, or are lactating during the study period.

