6 STUDY FLOWCHART

Population: Women 18 years + with bilateral breast cancer or pathological gene mutation

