Surgeons currently employ both intra-operative dissection techniques; therefore, this is not a new intervention; yet, importantly, there is no such novel study design known in the literature.

Therefore, CI with a team of engineers has been working on a device that surgeons can wear that will spread surgeons passively (without fatigue and trauma to their fingers) and at the same time, the extenders will increase reach where fingers can't. This will be an alternative to the retractors.

Whilst seeking funds for the development of the potential solution, it was suggested to gather some objective clinical evidence to demonstrate the difference in trauma caused to the tissues due to both of the existing surgical practices (retractors versus fingers-based).

This prospective case-control study represents an opportunity to compare tissue perfusion during breast mastectomy when using metal retractors versus fingers to lift the tissue. This study does not propose a new surgical technique or use a new instrument.

Differences in tissue perfusion between the two sides in the same patient (so there are no patient confounding factors) will help demonstrate the perceived problem objectively. The outcome of this study will establish the difference in trauma caused to the breast tissues due to current surgical practices, consequently, help improve intra-operative dissection techniques and reduce post-surgery infection and in addition, help to build an evidence-based case for the possible innovation of a new device to aid surgeons during this type of surgery.

In immediate breast reconstruction, the skin envelope with or without nipple must be preserved/spared (skin/nipple sparing mastectomy) after the removal of underlying breast tissue. However, mastectomy removes the dominant blood supply through the breast tissue, so the spared skin needs to survive on smaller blood vessels (capillary network) travelling along the skin's surface.

Tissue perfusion is the blood flow and oxygen supply to tissues, including the skin. Even brief periods of compromised perfusion to the tissue can lead to irreversible harm and complications. Currently tissue flap perfusion for mastectomies (simple, skin and nipple sparing), localised perforator flaps and larger pedicled (LD flap) or anastomotic (DIEP) flaps are assessed by reviewing capillary refill, warmth, and serial patient reviews. There are no additional methods for actual real-time visualisation of the tissue's vasculature.

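### The exclusion for radiotherapy to one breast depends on why the mastectomy is done, so some women with one irradiated breast can enter the between-breast comparison

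*Protocol*

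**What the plan says.** Section 11.2 lists as an exclusion "Previous unilateral breast radiotherapy (if mastectomy is for local recurrence"). No other criterion deals with radiotherapy to one breast. The next bullet covers earlier significant surgery on one breast, but only where it is "judged by the recruiting/operating surgeon to have adversely affected breast supply on that side". It does not mention radiotherapy.

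Section 11.1 admits women "Needing bilateral mastectomy for breast cancer or for risk reduction", and names previous mantle radiotherapy for lymphoma among the risk-reduction reasons. The same list, all of which must be met, also contains "Bilateral breast cancer". The flowchart in section 6 joins the two routes with an or: "Population: Women 18 years + with bilateral breast cancer or pathological gene mutation". Section 11.4 describes how risk-reduction patients are recruited. Section 11.2 also excludes "Unilateral breast cancer", without saying whether a past, treated cancer counts.

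Section 7 justifies the design by the within-patient comparison: "Differences in tissue perfusion between the two sides in the same patient (so there are no patient confounding factors"). Technique is fixed by side (8.1 and 12.2.1): the right breast is operated on first without retractors, and the left second with retractors only. The primary endpoint (10.1) is the between-breast difference in D, the change in perfusion from T1 to T2.

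**The concern.** The within-patient comparison works only if a woman's two breasts are alike apart from technique. The surgery bullet shows that the protocol means to keep out women whose two sides differ in blood supply, and it does so whatever the indication. The radiotherapy bullet has the same purpose but is tied to one indication, and no reason is given. Whether a breast was irradiated does not depend on why it is now being removed.

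If irradiated skin responds differently to dissection, that difference enters the between-breast contrast in D directly. Subtracting T1 removes only a constant baseline gap. The per-breast pain comparison lacks even that protection, because the schedule in Appendix 1 has no pre-surgery pain score.

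**Working it through.** **1. Who passes the criteria as written**

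- *New primaries in both breasts, one breast irradiated earlier.* She has bilateral cancer (11.1), she is not a unilateral case (11.2), and her mastectomy is not for local recurrence. The radiotherapy bullet does not exclude her. This holds on either reading of 11.1.
- *A risk-reduction patient irradiated earlier on one side.* Her mastectomy is not for local recurrence, so the bullet does not exclude her. She enters only if 11.1 is read as cancer or risk reduction, as sections 6 and 11.4 do, and if a past treated cancer does not count under "Unilateral breast cancer". Read literally, the bilateral-cancer line in 11.1 would bar her.
- *A new primary on one side only.* She is excluded as a unilateral case, so this route is closed.

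**2. The plan's own figure**

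Inputs from 17.1: difference 10, SD 25, one-sided 10% level, power 80%, n = 30. I take the SD to be that of the between-breast difference in D.

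- Normal approximation: n = [25 × (1.2816 + 0.8416) / 10]² = 28.2, rounded up to 29.
- Noncentral t: n = 29 gives 79.97% and n = 30 gives 81.0%. The stated 30 is therefore reproduced as a paired, one-sided test. The noncentrality at n = 30 is 10 / (25/√30) = 2.19, and the critical value is t(29) = 1.311.

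**3. Effect of admitting such women**

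The documents give neither input, so both are assumptions: k = 3 to 6 of 30 women with one irradiated breast, and an extra loss e = 10 to 20 points in D on that side. Take the contrast as D(right) minus D(left), so that a positive value means the retractor side did worse. An irradiated left breast adds e to a woman's contrast, and an irradiated right breast subtracts e.

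*Irradiated side random (left or right equally likely), simulated with 400,000 trials per cell:*

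| k | e | Type I error | Power at 10 points |
|---|---|---|---|
| 3 | 10 | 10% | 80.5% |
| 6 | 10 | 10% | 80% |
| 3 | 20 | 10% | 79% |
| 6 | 20 | 10% | 77% |

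The expected shift is zero. The power loss comes from added variance: the SD becomes √(25² + e²k/30), which is 25.2 for k = 3, e = 10 and 26.6 for k = 6, e = 20.

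*Chance imbalance in one trial.* The SD of the shift is e√k/30. That is 10 × 1.73/30 = 0.6 points at the low end and 20 × 2.45/30 = 1.6 points at the high end. The largest possible shift, with every irradiated breast on the same side, is e × k/30: from 10 × 3/30 = 1 point to 20 × 6/30 = 4 points, against a 10-point target.

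*Extremes, all on one side (same simulation):*

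| k | e | Shift | Type I error, all left | Power, all right |
|---|---|---|---|---|
| 3 | 10 | 1 | 14% | 74% |
| 3 | 20 | 2 | 19% | 66% |
| 6 | 10 | 2 | 19% | 66% |
| 6 | 20 | 4 | 31% | 48% |

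A noncentral-t approximation gives 32% in place of 31% in the last row. With equally likely sides, the chance that all are left-sided is (1/2)³ = 1/8 for k = 3 and (1/2)⁶ = 1/64 for k = 6.

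**The case against.** The strongest reply concerns size. A reader might infer from the fixed allocation of technique to side that irradiated breasts bias the trial systematically towards finding retractors worse, with a false-positive rate of 14% to 31%. The documents do not support that. Nothing in them links earlier radiotherapy to the left or right breast. Without such a link the type I error stays at about 10%, and the expected cost is roughly half a point to four points of power. This part of the reply stands.

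A reader might also infer that the bullet excludes almost nobody, because a local recurrence in one breast would usually be caught as a unilateral cancer. That is a claim about clinical frequency for which the protocol gives no figure. All that can be said is that the two bullets may overlap.

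Three further points narrow the concern without removing it:

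- The surgery bullet lets the surgeon exclude a woman whose earlier breast surgery impaired the blood supply, and 11.4 adds a general judgement of suitability by the clinical team. Both are discretionary, and neither mentions radiotherapy.
- The risk-reduction route depends on a non-literal reading of 11.1 and on a term that is not defined. The bilateral new-primary route does not, but it needs a specific history: cancer in both breasts now, earlier radiotherapy to one only, and classification as a new primary.
- The bracket may have been meant to explain when such radiotherapy arises. A site applying the word if must still treat it as a condition. If it was only explanatory, removing it loses nothing.

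**Conclusion.** The point holds as a gap in eligibility. The stated rule makes the exclusion depend on indication, and at least one kind of woman with a single irradiated breast passes every criterion. The statement in section 7 that no patient confounding remains does not hold for her.

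The likely effect is modest. Under the assumptions above (3 to 6 of 30 women, 10 to 20 points, side random), type I error is about 10% and power about 77% to 81%, against 81%. A chance imbalance could move the estimate of a single trial by at most 1 to 4 points. Only the all-one-side extremes give a type I error of 14% to 31% or power of 74% down to 48%. The true number of such women may be smaller than assumed, and the size of any differential response is unknown. Severity is minor to moderate.

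**What to change.** In 11.2, delete the bracketed condition so that previous radiotherapy to one breast excludes for any indication. Mantle radiotherapy, which 11.1 admits, is unaffected.

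This is a one-line amendment. It needs no new procedure, since medical history is already reviewed at eligibility (11.6), and it leaves n = 30 unchanged. The cost is that a few previously irradiated second-primary or risk-reduction patients become ineligible, so recruitment may be slightly slower.

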11.3 Co-enrolment Guidance

Enrolment into other ethically approved clinical trial(s) or studies is allowed, where coenrolment is permitted as part of the corresponding trial or study protocol provided there is no conflict of interest to PerfACT. It is the responsibility of the participating clinical trial/study Investigator to ensure oversight of co-enrolment throughout the PerfACT study. Questions regarding co-enrolment should be directed to a member of the PerfACT Study Management Group.

11.4 Patient Identification and Recruitment

Women that are due to undergo a double mastectomy with immediate reconstruction as part of breast cancer treatment will be identified during MDTs and will be approached and given a brief description of the clinical study by their treating clinician and asked if they would like to discuss the study further with a member of the research team. This will be recorded by the treating clinician in the medical notes. Patients who are referred by the genetics or family history team to the breast unit for consideration of risk reduction mastectomy will be identified at the point of receipt of referral by the breast surgeon or the breast care nursing team within participating units and flagged up to the research team.

The process for trial recruitment in this study is as follows:

- The investigating breast team will identify potentially suitable breast cancer patients at the specialist Breast multidisciplinary team (MDT) meeting.
- Risk reduction patients will be identified by the Clinical Genetics Team and highlighted to the PI or another member of the research team.
- Patients will attend an initial outpatient appointment at the surgical Breast clinic.
- At this appointment, the patient will be seen jointly by a surgeon and a research team member.
- Standard treatment options will be explained to the patient first.
- If the clinical team feel that the patient is suitable for the trial, the trial option will also be explained to the patient.
- If the patient expresses an interest in participation, they will be given a copy of the patient information sheet (PIS) to take away and review.
- The study research team will phone the patient later (minimum 24 hours) to ascertain whether she wishes to participate.
- If the patient agrees to participate, written informed consent will be obtained before

commencing study specific procedures.

11.5 Patient Informed Consent

The Patient Informed Consent Form will be approved by a Research Ethics Committee (REC) and must follow GCP, local regulatory requirements and legal requirements. The Investigator or designee must ensure that each study patient is fully informed about the nature and objectives of the study and possible risks associated with their participation.

The Investigator or designee will obtain written informed consent from each patient before any study-specific activity is performed. The Investigator will retain the original of each patient's signed informed consent form in the Investigator Site File (ISF).

As this is a low-risk, non-interventional study, patients may consent to take part on the same day as being offered the opportunity to participate. However, they must be given sufficient time

to read the PIS, consider taking part in the study and ask any questions before consenting. The Principal Investigator may delegate responsibility for consenting patients to appropriately trained healthcare professionals (including research nurses and practitioners) who may not be medical staff if this is accepted local practice. In order to limit risks to patients, including faceto-face contact or to negate additional hospital visits, consent can be obtained remotely. Several options will be considered acceptable:

• Verbal consent witnessed on speakerphone by two members of the research team. The consent form will be signed and dated by the two research team members and subsequently also signed by the patient at the next available opportunity.

• Consent form to be sent to the patient by mail or electronically, signed and dated by the patient and returned by mail or electronically, to be countersigned by a member of the research team.

• Email confirmation of consent sent from the patient's personal email address; the consent form will be signed and dated by a research team member and subsequently signed by the patient at the next available opportunity. The patient's email will be filed with a copy of the consent form.

In all remote consenting scenarios, the investigator is requested to document the rationale for remote consenting and the method planned/undertaken. In the case of remote consent, it is recognised that the date of the research team's signature may not always match that of the patient's signature.

Should a patient require written or a verbal translation of the trial documentation, it is the responsibility of the individual Investigator to use locally approved translators. Copies of translated documents must be provided to the central coordination team for filing in the Trial Master File (TMF).

Any new information that becomes available which might affect the patient's willingness to continue participating in the study will be communicated to the patient as soon as possible.

Study-specific procedures will only be performed after patients have consented to participation and signed the informed consent form.

11.6 Patient Eligibility Requirements

After patient informed consent has been obtained, the research team will confirm the eligibility of the patient by reviewing the following:

• Concomitant medications

- Medical history
- Review of most recent SoC pre-operative blood results as evidence of adequate liver and renal function
- Review of SoC pre-operative pregnancy test for women of childbearing potential

Within 28 days prior to registration, it must be verified that the patient satisfies all protocol eligibility criteria.

11.7 Patient Registration

Eligibility requirements documented in sections 11.1 and 11.2 must be met before registering a patient in this study. Only consenting patients who meet the eligibility requirements of the study at screening will be registered.

The following data will be required in order to enrol the patient:

- Confirmation that the patient satisfies all the eligibility criteria
- Year of birth
- Date of signed informed consent

Once it has been confirmed by the Investigator or suitably trained and delegated medically qualified member of the trial team that a patient meets the eligibility criteria, the investigator or designee must complete the registration electronic CRF in the REDCap[™] database (see the eCRF completion guidelines for instructions).

A unique study ID will be assigned to the patient, and this should be used in all future correspondence and on all patient-related documents.

12 PROCEDURES AND ASSESSMENTS

Refer to Section 26.1: Appendix 1 for Schedule of Assessments.

Patients will be clinically assessed throughout the study as per local practice.

Clinical assessments may be done remotely by telephone or videoconferencing, as appropriate and as per local practice.

Surgery-related adverse events will be recorded at each clinic visit from the point of surgery until the end of the 30-day follow-up period.

12.1 Pre-Surgery

Those patients who meet all eligibility criteria as per sections 11.1 and 11.2 and have been registered into the study will be asked to complete the BREAST-Q Version 2.0[©] Reconstruction Pre-operative Scales questionnaire, modules 8 and 7, prior to their surgery visit.

12.2 Surgery Visit

Registered patients will undergo surgery in accordance with local NHS timelines.

12.2.1 Surgery Procedure

The mastectomy with immediate reconstruction will be undertaken as per usual local procedures. Consented patients will undergo surgery and have sequential intra-operative fluorescence imaging assessments on each breast, whereby a fluorescent Indocyanine Green (ICG) dye will be injected intravenously and then detected using the Stryker's SPY-PHI handheld imager device to provide tissue perfusion measurements. The ICG dye will be administered intravenously as a bolus injection at the recommended dose of 0.1-0.3mg/kg body weight as per the manufacturer's guidelines for tissue perfusion diagnostics detailed in the ICG dye SmPC.

Right breast (Non-Retractor Technique)

The operating surgeon will first conduct the mastectomy procedure in the right breast using the non-retractor (finger dissection) technique to lift the breast tissue.

At the beginning of the mastectomy procedure, (defined as pre-incision on table and referred to as time TR1), and once confirmed that the fluorescent imager is ready to use, working and in hand, the surgeon will request that the ICG dye injection be administered to the patient. Once the dye is visualised, two tissue perfusion relative values (%) and the time in HH: MM (24hr format) will be taken and recorded. The first value will be the worst tissue perfusion relative value (%) observed in the 10x10cm area surrounding the incision, and the second value will be the best tissue perfusion relative value (%) observed anywhere in the breast.

The surgeon will then commence the mastectomy procedure and continue with the nonretractor (finger dissection) technique for as long as is comfortably possible and until finger fatigue prevents using this technique any longer. At this time point (referred to as TR2), the process of the ICG dye injection and two tissue perfusion measurements will be repeated as described for TR1.

After time point TR2 the surgeon will complete the mastectomy procedure using retractors to lift the breast tissue and the final ICG dye injection and two tissue perfusion measurements

will be completed at the end of the mastectomy procedure (defined as post-mastectomy before wound closure and referred to as time TR3).

In summary, the surgeon will request that the ICG dye be administered to the patient, after confirming the fluorescent imager is ready to use, working and in hand at the following three time points:

- TR1- beginning of mastectomy procedure, defined as pre-incision on table
- TR2- when the surgeon switches from finger dissection technique to metal retractors
- TR3- end of mastectomy, defined as post-mastectomy before wound closure

At each time point (TR1, TR2 & TR3), two tissue perfusion relative values (%) and the time in HH: MM (24hr format) will be taken and recorded. The first value will be the worst tissue perfusion relative value (%) observed in the 10x10cm area surrounding the incision, and the second value will be the best tissue perfusion relative value (%) observed anywhere in the breast.

Left Breast (Retractor Technique)

The operating surgeon will then conduct the mastectomy procedure in the left breast using metal retractors **only** from the beginning until the end of the procedure.

The surgeon will request that the ICG dye be administered to the patient, after confirming the fluorescent imager is ready to use, working and in hand at the following three time points:

- TL1- beginning of mastectomy procedure, defined as pre-incision on table
- **TL2** at the same time point that the surgeon switched from using fingers to metal retractors in the right breast (Time in mins = Right breast TR2 –Right breastTR1)

For example: If surgeon switched from the non-surgical (finger dissection) technique to retractors after 30 minutes in the right breast, then the tissue perfusion measurements in the left breast at time point TL2 will be taken 30 minutes after the beginning of the mastectomy procedure TL1 in the left breast.

• TL3- end of mastectomy, defined as post-mastectomy before wound closure

At each time point (TL1, TL2 & TL3), two tissue perfusion relative values (%) and the time in HH: MM (24hr format) will be taken and recorded. The first value will be the worst tissue perfusion relative value (%) observed in the 10x10cm area surrounding the incision. The second value will be the best tissue perfusion relative value (%) observed anywhere in the breast.

